#### **4.3. Protocol Deviations**

Any protocol deviations were reported to the Health Research Ethics Committee - Faculty of Medicine Universitas Indonesia and Cipto Mangunkusumo Hospital (HREC-FMUI/CMH).

#### **4.4. Compliance**

We will report the adherence to the supplementation for both groups based on the remaining supplements returned by the participants every month and verified through a monthly compliance record filled out by both subjects and field workers.

#### **4.5. Concomitant Therapies**

Concomitant interventions, including the use of other medicines, were documented using compliance records completed by both participants and field workers, capturing the type, duration, and frequency of use. These records were reviewed and summarized by the SP coordinator and reported to the DSMB.

## 5. ANALYSIS OF THE PRIMARY OUTCOME(S)

### 5.1. Main Analysis

We will perform all analyses after the last participant in the follow-up study has completed their visit. We will review the characteristics of the study sample as blinded cohort. First, we will use fake IDs and scrambled group code to write the script for analysis and create dummy tables and figures. Once the script, tables, and figures are ready, we will insert the correct IDs with blinded group code (e.g., A vs. B) and create the draft of the interpretation of the results for each case (e.g., if “A” is the Control group vs. if “A” is the Intervention group). We will finally reveal the group assignments after all authors have reviewed and approved the results for the primary outcomes. Unblinded analyses will be performed for secondary analyses, such as effect modification and subgroup analyses.

For all outcomes, the primary analysis to answer each objective will be a minimally adjusted model controlling only for child age at assessment and the randomization stratification factors (maternal education and municipality economic status). In secondary analyses, we will estimate adjusted parameters by including additional covariates—baseline characteristics, as well as post-enrollment and follow-up variables—in addition to those included in the primary analyses.

Unless otherwise specified, we will use two-sided confidence intervals at the 0.05 significance level for all analyses. For example, we are not powered to conduct subgroup/effect-modification analyses, so these secondary objectives will be exploratory and considered significant at the  $\alpha=0.10$  level. All hypothesis testing in this analysis plan is based on a two-sided superiority framework.

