Both groups consumed the supplements from the 2nd trimester of pregnancy until 6-months postpartum, regardless of their breastfeeding status. Omega-3 FAs supplementation began at 22 weeks of pregnancy, while probiotics/placebo supplementation started at 26 weeks. The gestational age for all subjects was assessed using ultrasonography at the nearest community health center or [name] General Hospital by trained general practitioners. These start times were chosen due to the late recognition of pregnancy in our population and therefore to ensure uniform initiation for all participants. Additionally, probiotics/placebo supplementation commenced during the third trimester because of limited evidence regarding probiotics use in pregnancy before this period. The placebo probiotics capsules were indistinguishable from the active capsules in appearance, taste, and odor. Likewise, the omega-3 capsules appeared identical across groups. All mothers in both groups also received psychosocial stimulation and healthy eating modules. These modules were delivered once during pregnancy (at 30–34 weeks of gestation) and twice during postpartum (between 0–1 month and between 1–2 months after birth). In the study sample, the majority of infants were breastfed, thus likely receiving DHA via their mother's breastmilk in addition to their prenatal exposure. Outcomes assessments were performed at 36–38 weeks of gestational age for fetal brain volume and when children reached the age of 4–6 months for Bayley-III, BERA, and eye-tracking assessments. All participants, outcome assessors, and field and research teams were blinded to the allocation of the intervention.

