#### 5.1.2 Baseline and fully adjusted analyses

We will also perform baseline and fully adjusted analyses with covariates for each outcome. First, we will perform bivariate analyses using the likelihood ratio test to test the association between the covariates with each outcome. Covariates with a p-value < 0.1 will be included in the adjusted analysis. Covariates with little variation in the study population (e.g., prevalence < 5%) will be

excluded. We will also evaluate the collinearity between potential covariates using the Variance Inflation Factor.

Potential covariates are listed below:

- Child sex: female or male
- Birth order: first-born or  $\geq$  second-born
- Municipality economic status: High or low
- Maternal height in centimeters
- Maternal pre-pregnancy BMI: BMI in  $\text{kg}/\text{m}^2$
- Maternal hemoglobin level at baseline in  $\text{g}/\text{L}$
- Maternal history of hypertension at baseline: With or without any history of hypertension
- Maternal age in years
- Maternal education: no education/incomplete primary/unknown, completed primary (6 years of formal education), completed secondary (9 years of formal education), completed greater than secondary
- Number of children under 5 yo in the household
- Number of household members
- Maternal marital status: monogamous marriage, polygamous marriage, or unmarried [single, divorced, widowed]
- Maternal occupation: housewife or working mother
- Paternal occupation: non-private sector and unemployed or private sector
- Monthly household expenditure in Indonesian Rupiah per month
- HOME inventory score (home environment)
- Screen time per day in minutes
- Staff members performing the assessment (for Bayley-III)

Two versions of adjusted analyses will be conducted as described below.

- Baseline adjusted model: This model will include covariates in minimally adjusted model and any of the following baseline covariates that are significantly associated at  $p < 0.1$  with the outcomes: child sex, birth order, maternal height, maternal pre-pregnancy BMI, maternal hemoglobin, maternal age, paternal age, paternal education, number of children under 5 yo in the household, number of household members, maternal marital status, maternal occupation, paternal occupation, household expenditure.

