## 5.3. Subgroup Analyses

As a secondary objective, we will assess for potential effect modification on the primary outcomes by testing an interaction term between the allocation group and the factors listed below. We will present the differences between the Intervention and Control groups stratified by the effect modifier if the interactions are significant at  $p < 0.1$ .

- **Child sex:** Biological differences, different care practices, or other psychosocial practices may modify the effect of interventions on girls vs boys.
- **Birth order:** Compared to second-born or greater (multiparous mothers), first-born tend to be smaller and may be associated with lower development, thus modifying the effect of interventions.

- **Maternal pre-pregnancy BMI status:** Overweight/obesity may change gut microbiota, including during pregnancy; therefore, it may modify the effect of our intervention between mothers with vs without overweight/obesity using a BMI cutoff of  $\geq 25$  kg/m^2.
- **Baseline maternal anemia:** Anemia during pregnancy has been associated with slower brain development, which may modify the effect of interventions between mothers with vs without anemia.
- **Baseline maternal age:** Biological differences, differential care practices, or differential social support networks due to different maternal age may modify the effect of the interventions on child development. We will first use maternal age as a continuous variable to test interactions. Significant interactions will be further examined with stratified analyses.
- **Baseline maternal education:** Maternal education has been consistently associated with child development and may modify the effect of interventions between mothers with low vs high education. We will use a cutoff of incomplete secondary schooling (<9 years of formal education) to define “low education” and secondary completion or greater as “high education”.
- **Baseline socioeconomic status:** We will categorize subjects based on monthly household expenditure into quintiles, then dichotomize into the highest quintile vs. the lowest four quintiles.
- **HOME Inventory score at 4–6 months:** Children from households with lower nurturing and stimulation of the home environment may have greater potential to benefit from the intervention. We will first use the HOME Inventory score as a continuous variable to test interactions. Significant interactions will be further examined with stratified analyses.

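### The primary model leaves out child sex; prespecifying it would be a small, nearly free gain in precision, though its omission is not an error

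*SAP*

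**What the plan says.** SAP 5.1 (Main Analysis) sets one primary model for all outcomes, "controlling only for child age at assessment and the randomization stratification factors". Section 5.1.1 repeats it as a linear regression on allocation group, age at assessment, maternal education and municipality economic status. The summary measures in Tables 2 and 3 carry the same terms, and the Secondary Outcomes section adopts the same approach.

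Child sex appears in four other places:

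- Table 1 lists it under Baseline.
- Section 5.1.2 lists it first among the potential covariates ("Child sex: female or male"). It is a candidate for the baseline adjusted model, which takes only covariates associated at p<0.1 "with the outcomes: child sex, birth order, maternal height, maternal pre-pregnancy BMI" and so on.
- Section 5.3 names it as an effect modifier: "Biological differences, different care practices, or other psychosocial practices may modify the effect of interventions on girls vs boys".
- The censoring-weight model in 5.2 uses the Table 1 baseline characteristics, which include sex.

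On timing, section 2.4 states that "Omega-3 FAs supplementation began at 22 weeks of pregnancy" and that probiotics or placebo started at 26 weeks. Sex is not a stratification factor (2.5). The SAP gives no reason for leaving sex out of the primary model and no figure for how strongly sex predicts any outcome.

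**The concern.** In a randomised comparison analysed by linear regression, adjusting for a variable that predicts the outcome and that treatment cannot affect narrows the confidence interval and leaves the mean difference being estimated unchanged. Child sex meets the second condition and may meet the first. It is already collected.

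Precision matters here because the design has little slack. Section 2.6 raised the target effect from 0.30 to 0.40 SD when anticipated attrition rose to 33.3% and funding was constrained. The trial ran from 2019 to 2022, so any further precision has to come from the analysis.

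The plan's present route to sex adjustment is also uneven. A p<0.1 screen applied outcome by outcome means that sex is adjusted for in some outcomes and not in others, partly by chance, and never in the primary estimate.

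**Working it through.** **Inputs from the SAP.** Difference 0.40 SD, α 0.05, power 0.80, attrition 33.3%, minimum N 300 (2.6); two-sided testing ("two-sided confidence intervals at the 0.05 significance level", 5.1); 157 randomised per arm (2.4).

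**Assumed.** R², the share of residual outcome variance explained by sex. The SAP does not give it, so a range is shown. The 0.40 SD is taken on the residual scale of the present model.

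**1. The plan's own figure.** By the normal approximation, n per arm = 2(1.960+0.842)²/0.40² = 98.1, so 99 per arm, 198 evaluable, and 198/(1−1/3) = 297. By the t-test, 100 per arm, 200 evaluable, and 200/(1−1/3) = 300. The stated 300 reproduces with no covariate gain counted.

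**2. Evaluable numbers.** The minimum target gives 300×(2/3)/2 = 100 per arm. The number randomised gives 157×(1−0.333) = 104.7, about 105 per arm.

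**3. What R² implies.** With an equal sex split and a standardised sex difference g, R² = (g²/4)/(1+g²/4), so g = 2√(R²/(1−R²)). R² of 1%, 2% and 5% correspond to g of about 0.20, 0.29 and 0.46 SD. R² of 10% and 15% would need 0.67 and 0.84 SD.

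**4. Power with sex added.** The residual SD is multiplied by √(1−R²). The non-centrality is 0.40/[√(1−R²)·√(2/n)], referred to a t distribution with 2n−5 degrees of freedom without sex and 2n−6 with it.

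| R² for sex | Sex difference | Power, 100 per arm | Power, 105 per arm | Narrower CI, 1−√(1−R²) |
|---|---|---|---|---|
| 0 (no sex term) | – | 80.4% | 82.2% | – |
| 1% | 0.20 SD | 80.8% | 82.6% | 0.5% |
| 2% | 0.29 SD | 81.1% | 83.0% | 1.0% |
| 5% | 0.46 SD | 82.3% | 84.1% | 2.5% |

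The gain in effective sample size, 1/(1−R²)−1, is 1.0%, 2.0% and 5.3%. One degree of freedom costs about 1/195 of the variance, so below an R² of about 0.005 the term brings no net gain.

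**5. Chance imbalance.** With 100 per arm and an even split, the between-arm difference in the proportion of boys has SD √(2×0.25/100) = 0.071. If sexes differ by 0.3 SD, an imbalance of that size moves the unadjusted estimate by 0.3×0.071 = 0.021 SD, against a standard error of √(2/100) = 0.141 SD.

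**6. The p<0.1 screen.** With 200 evaluable and 100 of each sex, approximating the likelihood ratio test by a two-sided t-test at α 0.10, the screen admits sex with probability 41% at 0.2 SD, 68% at 0.3 SD and 94% at 0.46 SD. It therefore misses a 0.2 SD difference 59% of the time and a 0.3 SD difference 32% of the time.

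**The case against.** The strongest reply is that this is a preference. The primary model is fully prespecified and consistent across the SAP, contains both stratification factors, and gives an unbiased estimate and a valid test without sex. That is correct.

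A reader might infer that the omission biases the primary comparisons, or that the plan gives up substantial precision on a known prognostic factor. The document supports neither. It names sex as one of eight possible effect modifiers, gives the same biological rationale for maternal age, and treats the association of sex with each outcome as something to be tested. Gains of 4 to 6 power points at R² of 10 to 15% would need sex differences well above the 0.40 SD treatment effect that the trial was sized for, so that end of the range should not be relied on. Nor is power pinned at 80.4%: at the SAP's own 157 per arm and 33.3% attrition it is about 82%.

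The SAP also deals with sex in part. Balance is checked in the retained sample (3.9), the weights use Table 1 variables (5.2), sex may enter the baseline adjusted model (5.1.2), and the treatment-by-sex interaction is tested (5.3). Where sex matters most, the screen will usually admit it. But these are a descriptive check, a sensitivity weighting, a screened secondary model and an exploratory test. None changes the primary estimate.

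A further caution stands. Handling unrecorded sex with a missing-category indicator would be unwise, because sex missing through loss after the MRI marks a post-randomisation event. Also, 5.1.1 allows ranked or ordinal analysis as a fallback. In an ordinal model an added covariate can change the effect being estimated, so the argument here is for the linear model.

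**Conclusion.** The point holds as an efficiency recommendation. Sex is collected, cannot be altered by the supplements and is potentially prognostic, yet it can reach only a secondary model through a data-driven screen.

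The benefit is small: about 0.4 to 2 power points at 0.40 SD, and a confidence interval 0.5% to 2.5% narrower, if sex explains 1% to 5% of residual variance. It is near zero for any outcome that sex does not predict, and it may differ across the MRI, Bayley-III, BERA and eye-tracking outcomes. These figures rest on an assumed R², an even sex split, and attrition at the SAP's 33.3%. The case for acting is that the cost is lower still.

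**What to change.** Before unblinding, amend 5.1, 5.1.1, the main analysis under Secondary Outcomes, and the summary measures in Tables 2 and 3. Add child sex as a prespecified fixed effect in the primary linear model for the primary outcomes, and likewise for the secondary outcomes, without the p<0.1 screen.

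For MRI participants whose sex was never recorded, keep them in the model by imputing a single value computed without regard to arm, for example the overall sample proportion, and state how many are affected. Report the model without sex as a sensitivity analysis.

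The cost is SAP wording, one degree of freedom per model, and the handling of any unrecorded sex, whose number the SAP does not give. No new data are needed.

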#### 5.1.1 Minimally adjusted analysis

We will evaluate the intention-to-treat (ITT) effects of the complete cases between allocation groups on each outcome. Our null hypothesis is that the estimated mean differences in the outcome do not differ significantly between the allocation groups. The null hypothesis will be rejected if the estimated mean differences are significantly different between the allocation groups.

We will fit linear regressions to assess the intervention’s effects on fetal brain growth and infant development, controlling for *Allocation Group*, *Child Age at outcome assessment*, *Maternal Education*, and *Municipality Economic Status* as fixed effects. We will first check the normality and homoscedasticity of residuals using the Shapiro-Wilk and Breusch-Pagan tests. If any model assumptions (e.g., linearity, constant variance, data heaping) are violated, we will explore data transformations before analysis (e.g., log transformation, square root transformation). If no suitable transformations can be made, the outcomes will be analyzed using ranked data or as an ordinal categorical variable in cases of extreme data heaping. We will also identify outliers using Cooks’ D, histograms, and scatter plots of the variables. Outliers that are possible will be kept, and sensitivity analyses will be completed with and without their inclusion. Outliers that are impossible (e.g. VPC Novelty Preference Score greater than one, IOWA mean latency less than zero, etc) will be corrected if possible or recorded to missing.

After fitting the models, we will estimate the mean differences of the variables of interest (e.g., *Allocation Group*) and conduct pairwise comparisons. We will not specifically evaluate model fit because it is not our primary interest.

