**Table 2. Primary Estimands**

Primary Estimand for Primary Analysis					
Population	Treatment	Outcome	Summary Measure	Potential intercurrent events	Strategy for intercurrent event
ITT	Initially randomised treatment (Intervention v. Control) and any subsequent changes to treatment over treatment period	Whole fetal brain volume in cm  at 36–38 weeks of gestational age (continuous)	Minimally adjusted mean difference (95%CI) between treatment arms in whole brain volume in cm  , adjusted for gestational age at assessment and the randomization stratification factors (maternal education and municipality economic status)	
 
1. Treatment discontinuation without study withdrawal
 
2. Early study withdrawal
 
3. Treatment non-compliance (intermittent or partial treatment adherence not resulting in treatment discontinuation)
 
4. Dose adjustment
 
	Treatment Policy for all intercurrent events - all observed values will be used, regardless of whether or not the subject had experienced the intercurrent event
		Bayley-III Cognitive score at 4–6 months: Z-score converted raw score of Bayley-III cognitive subscale (continuous)	Minimally adjusted mean difference (95%CI) between treatment arms in Bayley-III cognitive score, adjusted for child age at assessment and the randomization stratification factors (maternal education and municipality economic status)		
		Bayley-III Cognitive composite score at 4–6 months: Score based on conversion of Bayley-III cognitive scaled score (continuous)	Minimally adjusted mean difference (95%CI) between treatment arms in Bayley-III cognitive composite score, adjusted for child age at assessment and the randomization stratification factors (maternal education and municipality economic status)		
		BERA absolute latencies at 4–6 months for wave I in ms (continuous)	Minimally adjusted mean difference (95%CI) between treatment arms in absolute latencies for wave I, adjusted for child age at assessment and the randomization stratification factors (maternal education and municipality economic status)		
		BERA absolute latencies at 4–6 months for wave III in ms (continuous)	Minimally adjusted mean difference (95%CI) between treatment arms in absolute latencies for wave III, adjusted for child age at assessment and the randomization stratification factors (maternal education and municipality economic status)		

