		BERA absolute latencies at 4–6 months for wave V in ms (continuous)	Minimally adjusted mean difference (95%CI) between treatment arms in absolute latencies for wave V, adjusted for child age at assessment and the randomization stratification factors (maternal education and municipality economic status)		
		BERA interpeak latencies at 4–6 months for wave I–III interval in ms (continuous)	Minimally adjusted mean difference (95%CI) between treatment arms in interpeak latencies for wave I–III, adjusted for child age at assessment and the randomization stratification factors (maternal education and municipality economic status)		
		BERA interpeak latencies at 4–6 months for wave III–V interval in ms (continuous)	Minimally adjusted mean difference (95%CI) between treatment arms in interpeak latencies for wave III–V, adjusted for child age at assessment and the randomization stratification factors (maternal education and municipality economic status)		
		BERA interpeak latencies at 4–6 months for wave I–V interval (central conduction time) in ms (continuous)	Minimally adjusted mean difference (95%CI) between treatment arms in interpeak latencies for wave I–V, adjusted for child age at assessment and the randomization stratification factors (maternal education and municipality economic status)		

	IOWA mean latency at 6 months	Minimally adjusted mean difference (95%CI) between treatment arms in IOWA mean latency, adjusted for child age at assessment and the randomization stratification factors (maternal education and municipality economic status)
	IOWA task error at 6 months	Minimally adjusted mean difference (95%CI) between treatment arms in IOWA task error, adjusted for child age at assessment and the randomization stratification factors (maternal education and municipality economic status)
	VPC novelty preference score at 6 months	Minimally adjusted mean difference (95%CI) between treatment arms in VPC novelty preference score, adjusted for child age at assessment and the randomization stratification factors (maternal education and municipality economic status)
	VPC mean familiarization fixation at months	Minimally adjusted mean difference (95%CI) between treatment arms in VPC mean familiarization fixation, adjusted for child age at assessment and the randomization stratification factors (maternal education and municipality economic status)

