## SECONDARY OUTCOMES

### 5.1 Main Analysis

For all secondary outcomes, we will apply the same analytical approach used for the primary outcomes, including both the primary and secondary analyses. The primary analysis will use a minimally adjusted model, controlling only child age at assessment and the randomization stratification factors (maternal education and municipality economic status). In the secondary analyses, we will estimate adjusted parameters by adding additional covariates—baseline characteristics as well as post-enrollment and follow-up variables—in addition to those included in the primary analysis.

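### Section 5.1.1 lets residual checks move a primary outcome to a transformed, rank or ordinal analysis, so the primary result need not be the mean difference that Table 2 declares

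*SAP*

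**What the plan says.** Table 2 declares the estimands. For whole fetal brain volume the measure is "Minimally adjusted mean difference (95%CI) between treatment arms in whole brain volume in cm" (cubed). For a typical eye-tracking outcome it is "Minimally adjusted mean difference (95%CI) between treatment arms in VPC novelty preference score". All 13 entries follow this pattern and none has an alternative measure.

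Section 5.1.1 starts from linear regression on arm, age at assessment and the two stratification factors. Its test is worded on the same quantity: "The null hypothesis will be rejected if the estimated mean differences are significantly different between the allocation groups". It then adds a data-driven path:

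- A check: "We will first check the normality and homoscedasticity of residuals using the Shapiro-Wilk and Breusch-Pagan tests".
- A first fallback: "If any model assumptions (e.g., linearity, constant variance, data heaping) are violated, we will explore data transformations before analysis", with log and square root given as examples.
- A second fallback, if no transformation suits: "the outcomes will be analyzed using ranked data or as an ordinal categorical variable in cases of extreme data heaping".
- A closing step: "After fitting the models, we will estimate the mean differences of the variables of interest", with no scale stated.

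The path belongs to the main analysis, not to the sensitivity analyses in 5.2. The Secondary Outcomes part extends it: "For all secondary outcomes, we will apply the same analytical approach used for the primary outcomes".

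**The concern.** A difference in logs, square roots or ranks, or an ordinal odds ratio, is not a mean difference in cubic centimetres, milliseconds or score points. If the checks flag an outcome, the SAP tells the analyst to leave the declared estimand. It does not say what replaces it, how to transform back, what makes a transformation suitable, or whether the untransformed estimate is still reported as primary.

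Two things are at stake. The trial could report primary results on several scales, chosen from the data, against a table that promises one. And a significant result on a fallback scale would be read, under the rejection rule of 5.1.1, as evidence of a mean difference, although it tests something else.

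**Working it through.** **Inputs from the SAP.** Section 2.6: effect 0.40 SD, alpha 0.05, power 0.80, attrition 33.3%, minimum 300. Section 2.4: 157 per arm. Section 5.1: a general two-sided 0.05 level, assumed here to cover the residual checks.

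**The plan's own figure.** Per arm, 2 × (1.960 + 0.842)² / 0.40² = 98.1, so 99, or 198 in total. 198 / (1 − 0.333) = 297, which agrees with 300. The sample size thus rests on a standardised mean difference. Evaluable numbers are 300 × 0.667 = 200, or 314 × 0.667 = 209; 200 is used below.

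**Can the named transformations be applied?** Section 2.7.2 and Table 2 define the Bayley-III cognitive score as a Z-score, which can be negative. Log and square root are undefined there. Among secondary outcomes, the IOWA cue indices in 2.7.4 are relative differences and can also be negative.

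**Do the scales answer the same question?** Assume lognormal arms with equal means and log-SDs 0.4 and 0.6. For mean 1, the log-mean is −s²/2:

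- Log-means: −0.08 and −0.18. The difference is −0.10.
- Ratio of geometric means: exp(−0.10) = 0.905.
- Probability that a value in the second arm exceeds one in the first: Φ(−0.10 / √(0.16 + 0.36)) = Φ(−0.139) = 0.445.
- Mean difference: 0.

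With 99 per arm, simulated rejection was about 5% for the mean difference and about 27% on both the log scale and ranks. With log-SDs 0.4 in both arms, all three rejected in 4.3–4.5% of runs.

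**Type I error of the whole rule.** The simulation had 100 per arm and a model with arm, age and two binary strata. One reading of the rule was coded: if Shapiro-Wilk or Breusch-Pagan gives p < 0.05, try log, then square root (accepted if both checks pass), then ranks. Arm means are equal throughout, so Table 2's null is true. Ranges cover separate sets of runs.

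| Error distributions (assumed) | Rule rejects |
|---|---|
| Same shape and spread in both arms, or normal with SD ratio 1.3 (24 settings) | 4.6–5.9% |
| Skewness 1.0, SD ratio 1.3 | 8.0–9.1% |
| Skewness 1.0, SD ratio 1.5 | 11–12.5% |
| Exponential, SD ratio 1.3 | 24% |
| Lognormal, log-SDs 0.4 v 0.6 | 26–28% |

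The untransformed model with HC3 standard errors rejected in 4.0–5.4% of runs in the first row and about 5% (4.1–6%) in the others. For 3,000 runs, the simulation standard error at 5% is √(0.05 × 0.95 / 3000) = 0.4 points.

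**How often would an outcome be flagged?** At 0.05 by either test: 9–10% with normal errors, 89–90% at skewness 0.63, 79–81% for t errors with 5 df, and 49–52% at SD ratio 1.3. If only Breusch-Pagan counts, the figures are 4–6% for every equal-variance shape and 45–47% at SD ratio 1.3. Flagged does not mean moved to ranks.

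**The case against.** **Such fallbacks are routine, and 5.1.1 still promises mean differences.** Many plans do contain them, but this one also tabulates its estimands, and the fallback leaves the table. The closing sentence names no scale, so after a log or rank step it would be met by a difference in logs or ranks.

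**Blinding protects the choice.** Section 5.1 has scripts written with fake IDs and scrambled group codes, then results reviewed under A/B codes before unblinding. This is a real safeguard. A reader might infer that the rule lets the team pick the scale that favours the intervention; the documents do not support that. Blinding does not settle what is estimated.

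**The test level is not missing.** A reader might say the checks have no level. Section 5.1's general 0.05 is a fair default, so the point does not rest on this.

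**The frequencies are assumptions.** This stands. The SAP gives no outcome distributions. Its examples of violations omit normality, although normality is tested. The log, square-root, rank order is only one reading of a loosely worded rule, and the ordinal route was not simulated.

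**HC3 does not cure a curved relation with age.** Correct. A prespecified non-linear age term would address that and leave the effect measure unchanged.

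**Conclusion.** The contradiction is in the text and needs no simulation: 5.1.1 allows a change of scale in the primary analysis, while Table 2 and the rejection rule of 5.1.1 are stated only as a mean difference. Nothing keeps the untransformed result as primary.

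On error control, two inferences should be avoided. One is that the rule generally inflates type I error. It stays near 5% when the arms share an error distribution, or differ only in spread with symmetric errors. The other is that error control is unaffected. When skewness and unequal spread occur together, rejection with equal means was about 9% to 28% in the four settings tried, against about 5% for HC3. Those sizes rest on assumed shapes, 200 evaluable infants, a 0.05 level for the checks and one reading of the rule. They show what can happen and do not predict this trial.

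The change should be made. Confidence is high in the contradiction, but not in any particular frequency of switching.

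**What to change.** In 5.1.1, state that the primary result for every primary and secondary outcome is the linear-model adjusted mean difference on the scale defined in section 2.7, with heteroscedasticity-robust standard errors (for example HC3), whatever the residual checks show. State that the checks are descriptive.

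Move transformed, rank and ordinal analyses to 5.2 as labelled sensitivity analyses for the primary outcomes, each with its measure named:

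- log: ratio of geometric means, only for outcomes that cannot be zero or negative;
- rank: probability that a value in one arm exceeds one in the other;
- ordinal: common odds ratio.

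Whole brain volume appears in both Table 2 and Table 3. Count it as primary, because the Secondary Outcomes part rules out sensitivity analyses for secondary outcomes.

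The cost is a paragraph of text and one option in the R code. In the simulations HC3 standard errors averaged 1.3% larger. Power given up against the fallback was under 1 point with normal errors, 2–5 points at skewness 0.63, 6–8 at skewness 1.0 or t with 5 df, and 16–20 for exponential errors. That extra power comes from testing a different quantity. Power for the planned 0.40 SD mean difference stayed at 77–81%, and the sample size does not change.
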